10.2 MANAGEMENT OF IMMUNE-RELATED ADVERSE EVENTS

Management of immune-related adverse event toxicities associated with anti-PD-1 mAbs are presented below. Ezabenlimab should be permanently discontinued for Grade 3-4 pneumonitis, Grade 3-4 adrenal insufficiency, Grade 4 diabetes mellitus, any grade encephalitis, Grade 4 hypophysitis, Grade 4 rash, Grade 3-4 or recurrent colitis of any grade, any recurrent Grade 3-4 AE, transaminase >5 times ULN or total bilirubin >3 times ULN (unless unequivocally attributable to another cause), inability to taper steroids to 10 mg or less prednisone or equivalent within 12 weeks, or persistent Grade 2-3 AEs that do not recover to Grade 1 or less within 12 weeks.

- Pneumonitis:
 - For Grade 2 events, treat with systemic corticosteroids. When symptoms improve to Grade 1 or less, steroid taper should be started and continued over no less than 28 days.
 - Add prophylactic antibiotics for opportunistic infections in the case of prolonged steroid administration.
 - For Grade 3-4 events immediately treat with i.v. steroids. Administer additional anti-inflammatory measures, as needed.
 - Ezabenlimab should be permanently discontinued for Grade 3-4 pneumonitis, inability to taper steroids to 10 mg or less prednisone or equivalent within 12 weeks, or persistent Grade 2 AEs that do not recover to Grade 1 or less within 12 weeks.
- Diarrhoea/Colitis:

Subjects should be carefully monitored for signs and symptoms of enterocolitis (such as diarrhoea, abdominal pain, blood or mucus in stool, with or without fever) and of bowel perforation (such as peritoneal signs and ileus).

 - All subjects who experience diarrhoea/colitis should be advised to drink liberal quantities of clear fluids. If sufficient oral fluid intake is not feasible, fluid and electrolytes should be substituted via i.v. infusion. For Grade 2 or higher diarrhoea, consider GI consultation and endoscopy to confirm or rule out colitis.
 - For Grade 2 diarrhoea/colitis that persists greater than 3 days, administer oral corticosteroids.
 - For Grade 3 or 4 diarrhoea that persists >1 week, treat with i.v. steroids followed by high-dose oral steroids.
 - For Grade 3 or 4 colitis, or recurrent colitis of any grade, permanently discontinue Ezabenlimab and immediately treat with i.v. steroids followed by high-dose oral steroids.
 - When symptoms improve to Grade 1 or less, steroid taper should be started and continued over no less than 28 days.
 - Ezabenlimab should be permanently discontinued for Grade 3-4 or recurrent colitis of any grade, inability to taper steroids to 10 mg or less prednisone or equivalent within 12 weeks, or persistent Grade 2-3 AEs that do not recover to Grade 1 or less within 12 weeks.
- Type 1 diabetes mellitus (if new onset, including diabetic ketoacidosis) Grade 3, or \geq Grade 3 hyperglycaemia, if associated with ketosis (ketonuria) or metabolic acidosis
 - For Type 1 diabetes mellitus Grade 3-4 or Grade 3-4 hyperglycaemia

- Insulin replacement therapy is recommended for Type I diabetes mellitus and for Grade 3-4 hyperglycaemia associated with metabolic acidosis or ketonuria.
- Evaluate subjects with serum glucose and a metabolic panel, urine ketones, glycosylated haemoglobin, and C-peptide.
- Ezabenlimab should be permanently discontinued for Grade 4 diabetes mellitus, any recurrent Grade 3 AE or persistent Grade 2-3 AE that does not recover to Grade 1 or less within 12 weeks.
- Hypophysitis:
 - For Grade 2 events, treat with corticosteroids. When symptoms improve to Grade 1 or less, steroid taper should be started and continued over no less than 28 days. Replacement of appropriate hormones may be required as the steroid dose is tapered.
 - For Grade 3 events, treat with an initial dose of i.v. corticosteroids followed by oral corticosteroids. When symptoms improve to Grade 1 or less, steroid taper should be started and continued over no less than 28 days. Replacement of appropriate hormones may be required as the steroid dose is tapered.
 - For Grade 4 events, permanently discontinue ezabenlimab, and treat with an initial dose of i.v. corticosteroids followed by oral corticosteroids. When symptoms improve to Grade 1 or less, steroid taper should be started and continued over no less than 28 days. Replacement of appropriate hormones may be required as the steroid dose is tapered.
 - Ezabenlimab should be permanently discontinued for Grade 4 hypophysitis, any recurrent Grade 3 AE, inability to taper steroids to 10 mg or less prednisone or equivalent within 12 weeks, or persistent Grade 2-3 AEs that do not recover to Grade 1 or less within 12 weeks.
- Hyperthyroidism or Hypothyroidism:

Thyroid disorders can occur at any time during treatment. Monitor subjects for changes in thyroid function (at the start of treatment, periodically during treatment, and as indicated based on clinical evaluation) and for clinical signs and symptoms of thyroid disorders.

 - For Grade 2 hyperthyroidism events (and Grade 3-4 hypothyroidism):
 - In hyperthyroidism, nonselective beta-blockers (e.g., propranolol) are suggested as initial therapy.
 - In hypothyroidism, thyroid hormone replacement therapy, with levothyroxine or liothyronine, is indicated per standard of care.
 - For Grade 3-4 hyperthyroidism
 - Treat with an initial dose of i.v. corticosteroid followed by oral corticosteroids. When symptoms improve to Grade 1 or less, steroid taper should be started and continued over no less than 28 days. Replacement of appropriate hormones may be required as the steroid dose is tapered.
 - Ezabenlimab should be permanently discontinued for any recurrent Grade 3-4 AE, inability to taper steroids to 10 mg or less prednisone or equivalent within 12 weeks, or persistent Grade 2-3 AEs that do not recover to Grade 1 or less within 12 weeks.

- Hepatic:
 - For Grade 2 events, monitor liver function tests more frequently until returned to baseline values (consider weekly).
 - Treat with i.v. or oral corticosteroids
 - For Grade 3-4 events, treat with i.v. corticosteroids for 24 to 48 hours.
 - When symptoms improve to Grade 1 or less, a steroid taper should be started and continued over no less than 28 days.
 - Ezabenlimab should be permanently discontinued for any recurrent Grade 3-4 AE, transaminase >5 times ULN or total bilirubin >3 times ULN (unless unequivocally attributable to another cause), inability to taper steroids to 10 mg or less prednisone or equivalent within 12 weeks, or persistent Grade 2-3 AEs that do not recover to Grade 1 or less within 12 weeks.
- Renal failure or nephritis:
 - For Grade 2 events, treat with corticosteroids.
 - For Grade 3-4 events, treat with systemic corticosteroids.
 - When symptoms improve to Grade 1 or less, steroid taper should be started and continued over no less than 28 days.
 - Ezabenlimab should be permanently discontinued for any recurrent Grade 3-4 AE, inability to taper steroids to 10 mg or less prednisone or equivalent within 12 weeks, or persistent Grade 2-3 AEs that do not recover to Grade 1 or less within 12 weeks.
- Adrenal insufficiency
 - Ezabenlimab should be permanently discontinued for Grade 3-4 adrenal insufficiency or persistent Grade 2 AEs that do not recover to Grade 1 or less within 12 weeks.
- Rash
 - Ezabenlimab should be permanently discontinued for Grade 4 rash, any recurrent Grade 3 AE or persistent Grade 2-3 AEs that do not recover to Grade 1 or less within 12 weeks.
- Encephalitis
 - Ezabenlimab should be permanently discontinued for any grade encephalitis.
- Infusion reactions:

Signs and symptoms usually develop during or shortly after drug infusion and generally resolve completely within 24 hours of completion of infusion. In the event of an infusion-related reaction \leq Grade 2, treat the symptoms accordingly with antihistamine or corticosteroids if needed, the infusion rate of study drug(s) may be decreased by 50% or interrupted until resolution of the event and re-initiated at 50% of the initial rate until completion of the infusion. In patients experiencing infusion-related reactions \leq Grade 2, subsequent infusions may be administered at 50% of the initial rate. If an infusion-related reaction is Grade 3 or higher in severity at any point during the study, permanently discontinue study drug(s).

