5.2.6.1.3 Adverse events of special interest

The term adverse events of special interest (AESI) relates to any specific AE that has been identified at the project level as being of particular concern for prospective safety monitoring and safety assessment within this trial, e.g. the potential for AEs based on knowledge from other compounds in the same class. AESIs need to be reported to the sponsor's Pharmacovigilance Department within the same timeframe that applies to SAEs, please see Section 5.2.6.2.2.

For this trial, infusion-related AEs, potential DILI events, hepatic injury, and qualifying irAEs, as defined in the treatment-specific Modules and Appendix [10.1](#), are AESIs.

Immune-related adverse events (irAEs)

Immune-related AEs are AEs associated with immunotherapy treatments that appear to be associated with the immune therapy's mechanism of action. These adverse reactions, which can be severe, may involve the gastrointestinal, skin, liver, endocrine, respiratory, renal, or other organ systems. All immune-related events are to be reported as AEs. Some irAEs also need to be reported as AESIs as defined by the sponsor in Appendix [10.1](#). If an Investigator determines a Grade 3 event of an AE that is not mentioned on the list of immune-related AEs, the Investigator should also report that event as an AESI.

Recommendations for the management of irAEs are presented in Appendix [10.2](#).

Infusion-related reactions

In the event of an infusion-related reaction \leq Grade 2, treat the symptoms accordingly with antihistamine or corticosteroids if needed. The infusion rate of ezabenlimab may be decreased by 50% or interrupted until resolution of the event and re-initiated at 50% of the initial rate until completion of the infusion. In patients experiencing infusion-related reactions \leq Grade 2, subsequent infusions may be administered at 50% of the initial rate. If an infusion-related reaction to trial medications is Grade 3 or higher in severity at any point during the study, permanently discontinue study drug(s).

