5.2.6.2.2 AE reporting to the sponsor and timelines

The Investigator must report SAEs, AESIs, and non-serious AEs that are relevant for the reported SAE or AESI, on the BI SAE form via secure e-mail connection or via fax immediately (within 24 hours) to [REDACTED] Safety Department:

- Secure email [REDACTED] mailbox:
[REDACTED] or
- Fax [REDACTED] safety fax number: [REDACTED]
[REDACTED]

For sites outside of the US, country-specific fax numbers will be provided in the ISF/study reference manual.

The same timeline applies if follow-up information becomes available. On specific occasions, the Investigator can inform [REDACTED] Safety Department upfront via telephone by calling [REDACTED] reporting phone number ([REDACTED]). This does not replace the requirement to complete and fax the BI SAE form.

With receipt of any further information about these events, a follow-up SAE form has to be provided. For follow-up information the same rules and timeline apply as for initial information.

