10. APPENDICES

10.1 IMMUNE-RELATED ADVERSE EVENTS OF SPECIAL INTEREST

Table 10.1: 1 Immune-related adverse events of special interest

This table defines immune-related AEs that must be reported as AESIs.

Immune-related adverse events of special interest
Pneumonitis (reported as an AESI if \geq Grade 2) 
• Acute interstitial pneumonitis• Interstitial lung disease• Pneumonitis
Colitis (reported as an AESI if \geq Grade 2 or any grade resulting in dose modification or use of systemic steroids to treat the AE) 
• Intestinal obstruction• Colitis• Colitis microscopic• Enterocolitis• Enterocolitis haemorrhagic• Gastrointestinal perforation• Necrotizing colitis• Diarrhoea
Endocrine (reported as an AESI if \geq Grade 3 or \geq Grade 2 and resulting in dose modification or use of systemic steroids to treat the AE) 
• Adrenal insufficiency• Hyperthyroidism• Hypophysitis• Hypopituitarism• Hypothyroidism• Thyroid disorder• Thyroiditis• Hyperglycaemia, if \geq Grade 3 and associated with ketosis or metabolic acidosis
Endocrine (reported as an AESI) 
• Type 1 diabetes mellitus (if new onset)

Immune-related adverse events of special interest

Hematologic (reported as an AESI if \geq Grade 3 or any grade resulting in dose modification or use of systemic steroids to treat the AE)

- Autoimmune haemolytic anaemia
- Aplastic anaemia
- Thrombotic thrombocytopenic purpura
- Idiopathic (or immune) thrombocytopenia purpura
- Disseminated intravascular coagulation
- Haemolytic-uraemic syndrome
- Any Grade 4 anaemia regardless of underlying mechanism

Hepatic (reported as an AESI if \geq Grade 2, or any grade resulting in dose modification or use of systemic steroids to treat the AE)

- Hepatitis
- Autoimmune hepatitis
- Transaminase elevations (ALT and/or AST)

Infusion Reactions (reported as an AESI)

- Allergic reaction
- Anaphylaxis
- [REDACTED] release syndrome
- Serum sickness
- Infusion reactions
- Infusion-like reactions

Neurologic (reported as an AESI)

- Autoimmune neuropathy
- Guillain-Barre syndrome
- Demyelinating polyneuropathy
- Myasthenic syndrome

Ocular (report as an AESI if \geq Grade 2 or any grade resulting in dose modification or use of systemic steroids to treat the AE)

- Uveitis
- Iritis

Renal (reported as an AESI if \geq Grade 2)

- Nephritis
- Nephritis autoimmune
- Renal failure
- Renal failure acute

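### Appendix 10.2 gives Grade 3-4 diarrhoea not diagnosed as colitis a longer wait before steroids (more than 1 week) than Grade 2 diarrhoea (more than 3 days)

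*Protocol*

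**What the plan says.** The diarrhoea/colitis part of Protocol Appendix 10.2 sets three steroid triggers:

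- Grade 2: "For Grade 2 diarrhoea/colitis that persists greater than 3 days, administer oral corticosteroids".
- Grade 3-4 diarrhoea: "For Grade 3 or 4 diarrhoea that persists >1 week, treat with i.v. steroids followed by high-dose oral steroids".
- Grade 3-4 or recurrent colitis: "For Grade 3 or 4 colitis, or recurrent colitis of any grade, permanently discontinue Ezabenlimab and immediately treat with i.v. steroids".

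On work-up it says: "For Grade 2 or higher diarrhoea, consider GI consultation and endoscopy to confirm or rule out colitis". On stopping steroids: "When symptoms improve to Grade 1 or less, steroid taper should be started and continued over no less than 28 days".

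Protocol Sections 4.2.1 and 5.2.6.1.3 both describe Appendix 10.2 as recommendations. The colitis group in Appendix 10.1 includes diarrhoea, which is an adverse event of special interest from Grade 2 upwards. Section 5.2.6.1.3 requires such events to reach the sponsor's "Pharmacovigilance Department within the same timeframe that applies to SAEs", and Section 5.2.6.2.2 sets that at 24 hours.

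**The concern.** One expects the wait before immunosuppression to shorten, or at least not lengthen, as an immune-related toxicity becomes more severe. Here it lengthens. Followed literally, the guidance tells a site to start steroids after 3 days of moderate diarrhoea but gives no steroid instruction for severe or life-threatening diarrhoea until a week has passed, unless someone has diagnosed colitis.

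The stake is patient safety. The same part of the appendix asks sites to watch for enterocolitis and bowel perforation, and Section 1.4 names the gastrointestinal system among those where most immune-related events were seen. The appendix sits in the Master protocol, so it serves every combination Module. Inclusion criterion 3 also uses the protocol's immune-related event guidelines as the standard for crossing over between Modules. No endpoint, sample size or analysis depends on the point.

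**Working it through.** The plan states no statistical figure to reproduce. The check is a comparison of the triggers, a count of days and a bound on frequency.

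**1. Triggers side by side (Appendix 10.2)**

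| Event | Wait before steroids | First day of instruction (onset = day 1) |
|---|---|---|
| Grade 2 diarrhoea/colitis | more than 3 days | day 4 |
| Grade 3-4 diarrhoea, not called colitis | more than 1 week | day 8 |
| Grade 3-4 or recurrent colitis | none | at diagnosis |

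The difference is 8 − 4 = 4 days: days 4, 5, 6 and 7.

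**2. Can the Grade 2 line be read as a floor for all grades?** No. The work-up line in the same list says Grade 2 or higher where that is meant. The Grade 2 steroid line does not, and Grade 3-4 diarrhoea has its own line with its own clock.

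**3. Does another rule fill the gap?** The permanent-discontinuation criteria cover Grade 3-4 or recurrent colitis, recurrent Grade 3-4 events, failure to taper and events persisting for 12 weeks. None starts steroids for a first episode of Grade 3-4 diarrhoea. Reporting as an event of special interest informs the sponsor but gives no treatment instruction.

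**4. Comparison with the rest of the appendix.** Grade 3-4 pneumonitis is treated immediately. The Grade 3-4 steroid instructions for hypophysitis, hyperthyroidism, hepatic and renal events have no persistence condition. Diarrhoea/colitis is the only entry with a persistence wait before steroids, and there the wait grows with severity.

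**5. Who is affected.** Patients whose diarrhoea reaches Grade 3-4 before any steroid is given and is not called colitis. A patient already on steroids for Grade 2 diarrhoea who then worsens is outside the gap, because taper starts only at Grade 1 or less.

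**6. The clock.** The text does not say from when persistence is counted. The 4-day figure assumes counting from onset. If counting restarts on reaching Grade 3, a patient at Grade 2 on days 1-3 and Grade 3 from day 4 has no instruction until day 4 + 7 = 11, so the gap could be longer.

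**7. Frequency (Section 1.4, 50 monotherapy patients)**

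- Diarrhoea of any grade: 0.14 × 50 = 7 patients.
- Grade 4 events of any kind: 0.04 × 50 = 2 patients, one with disease progression and one with sepsis. Grade 4 diarrhoea of any cause is therefore 0/50.
- Grade 3 diarrhoea of any cause is not given. It lies between 0 and 7 of 50 (0% to 14%). The upper end is unlikely, because most of the frequent events were Grade 1 or 2.
- Immune-related Grade 3-4 diarrhoea: 0/50, because the only Grade 3 immune-related event was an AST increase. The exact two-sided 95% upper bound is 1 − 0.025^(1/50) = 0.071, or 7.1%. This counts only events classed as immune-related.

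**The case against.** The strongest reply is that the lines do not cover like-for-like groups. At Grade 2 the text pools diarrhoea with colitis. At Grade 3-4 it separates them, treats colitis at once and leaves a remainder whose cause is less certain. A longer wait for that remainder could be deliberate. This explains the order only in part: Grade 2 diarrhoea without colitis is in the pooled group and still gets the shorter wait, so uncertainty about the cause cannot justify the longer wait at the higher grade alone. The work-up meant to resolve the uncertainty is optional and has no deadline.

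Several points on weight do stand. The appendix is advisory, and nothing in it forbids earlier steroids. A diagnosis of colitis moves the patient to immediate treatment. The sponsor learns of the event within 24 hours. Once started, the Grade 3-4 regimen is the more intensive one, so only the timing is inverted. The Module protocols, which may hold further guidance, are not among the documents. The frequency figures bound the affected group and do not measure it, since they do not isolate events that are without colitis, untreated with steroids and longer than 3 days. These points lower the weight but do not put the triggers in the right order.

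The correction can also be criticised: it still allows a 3-day wait at Grade 3-4, and the 3 days is taken from the Grade 2 line with no other source in the documents. That is a fair description. Matching the Grade 2 trigger is the least change that removes the inversion, and the sponsor's clinicians may prefer a shorter wait.

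**Conclusion.** The concern holds. In the current text the steroid trigger for Grade 3-4 diarrhoea not diagnosed as colitis comes later than the trigger for Grade 2 diarrhoea, and nothing else in the supplied documents gives an earlier start for a first episode. The gap is 4 days if persistence is counted from onset with onset as day 1, and may be longer if it is counted from reaching Grade 3. Few patients are likely to meet it on the monotherapy data. How many would on the combinations cannot be judged from the documents. This is a safety wording point that should be corrected. It has no statistical consequence.

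**What to change.** Amend only the Grade 3-4 diarrhoea line of Appendix 10.2, to this effect: at Grade 3 or 4, begin i.v. steroids and follow with high-dose oral steroids once diarrhoea of at least Grade 2 has lasted more than 3 days, or sooner if colitis is suspected. Counting from the onset of Grade 2 or higher also settles the undefined clock. The Grade 2 line and the immediate-treatment line for Grade 3-4 or recurrent colitis stay as they are, so confirmed Grade 3-4 colitis still leads to permanent discontinuation.

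The cost is one line in a protocol amendment. The clinical downside is somewhat earlier steroids, with a taper of at least 28 days, in a few patients, some of whose diarrhoea may turn out not to be immune-related. There is no statistical cost.

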10.3 PHARMACOKINETIC METHODS AND ANALYSES

Methods and procedure for handling blood samples are presented in the Laboratory Manual for the individual Modules.

11. DESCRIPTION OF GLOBAL AMENDMENT(S)

This is the original protocol.

11.1 GLOBAL AMENDMENT 1

Date of amendment	7 MAY 2019
EudraCT number	2018-002344-81
EU number	
BI Trial number	BI 1381-0009
BI Investigational Medicinal Product(s)	See Modules
Title of protocol	An open-label, Phase II, platform trial evaluating safety and efficacy of multiple BI 754091 anti-PD-1 based combination regimens in PD-(L)1 naïve and PD-(L)1 pretreated patient populations with advanced and/or metastatic solid tumours who have had at least one line of systemic therapy
To be implemented only after approval of the IRB / IEC / Competent Authorities	X 
To be implemented immediately in order to eliminate hazard – IRB / IEC / Competent Authority to be notified of change with request for approval	
Can be implemented without IRB / IEC / Competent Authority approval as changes involve logistical or administrative aspects only	
Section to be changed	Synopsis - Main inclusion and exclusion criteria
Description of change	Patients moving from one module to another must have prior irAEs resolved to a degree that would allow for restart of checkpoint inhibitor therapy according to the irAE management guidelines in the protocol.
Rationale for change	An additional inclusion criteria was added and included in the list of main inclusion and exclusion criteria to highlight it.

Section to be changed	Synopsis - Main inclusion and exclusion criteria
Description of change	More than A maximum of one anti-PD-(L)1-based treatment regimen prior to entering study, more specifically defined in the modules.
Rationale for change	To help clarify the criteria
Section to be changed	Synopsis - Main inclusion and exclusion criteria
Description of change	
Active autoimmune disease or a documented history of autoimmune disease, except vitiligo or resolved childhood asthma/atopy, or a patient who was permanently discontinued removed from previous anti-PD-1 or anti-PD-L1 therapy because of a severe immune-related adverse event (irAE).
Rationale for change	To help clarify the criteria
Section to be changed	Synopsis - Duration of Treatment
Description of change	The patient must sign an approved ICF for the subsequent Module, be screened prior to entering the new Module, and must meet all Master and Module-specific inclusion criteria. The transition time between Modules (last dose of previous Module and screening visit of subsequent Module) will be a maximum of 2 months. Patients will be allowed multiple crossovers into subsequent Modules.
Rationale for change	The additional text provides further detail about how a crossover to another Module after progression on their previous treatment Module.
Section to be changed	1.2 Drug Profile
Description of change	BI 754091 will be combined with other agents in each of the multiple Modules.
Rationale for change	“Multiple” was removed from the description of modules to avoid implying there would be an unlimited number of modules in the study.
Section to be changed	1.4 BENEFIT – RISK ASSESSMENT
Description of change	BI 754091 is currently being tested in patients in the BI 1381.1 clinical trial. Preliminary clinical safety information indicates that BI 754091 monotherapy in 39 patients with advanced metastatic cancer is well tolerated with no reported dose limiting toxicities (DLTs), treatment related SAE or treatment related deaths. Preliminary efficacy analyses indicate that there are 5 patients with partial response (PR) and 17 patients with disease stabilization on BI 754091 monotherapy in the trial 1381.1. The PRs were reported in two patients with triple negative breast cancer,

	
one patient with ovarian cancer, one patient with renal cancer, and one patient with stomach cancer. All of these PRs occurred in patients receiving the 240 mg q3w dose of BI 754091 (BI 754091 Investigator Brochure).
 
As of 30-November-2018, 50 patients with advanced/metastatic solid tumours have been treated with BI 754091 as monotherapy in the 1381.1 trial.
 
The most frequently reported AEs (reported in >10% of the patients) were fatigue (40%), nausea (28.0%), decreased appetite (18.0%), arthralgia (16.0%), cough (16.0%), abdominal pain (14.0%), constipation (14.0%), diarrhoea (14.0 %), vomiting (14.0), back pain (12.0%) and dyspnoea (12.0%). Headache, hypokalaemia, muscular chest pain, myalgia, pruritis and rash, each occurred at a frequency of 10.0%. The majority of these AEs were CTCAE Grade 1 and 2.
 
Grade 3 and 4 AEs were reported in 38.0% and 4.0% of patients, respectively. Of the Grade 3 events, only the AST elevation event was reported as related to trial drug. The reported Grade 4 AEs were 1 (2.0%) case of disease progression and 1 (2.0%) case of sepsis, neither of which was deemed treatment related.
 
Consistent with the similar drug class labels, most irAEs were reported in the GI, skin and endocrine system organ class (SOCs). The majority of the irAEs were Grades 1 or 2; the only Grade 3 irAE was AST increase.
 
Preliminary efficacy analyses for study 1381.1 indicate that there have been 6 patients with partial response (PR) and 20 patients with stable disease (SD) as best response on BI 754091 monotherapy. The PRs were reported in two patients with triple negative breast cancer, one patient with fallopian tube cancer, one patient with renal cancer, one patient with stomach cancer and one patient with endometrial cancer. All of these PRs occurred in patients receiving the 240 mg q3w dose of BI 754091.
 
A similar safety profile of BI 754091 monotherapy was observed in 6 Japanese patients with solid tumours evaluated in the Asian trial 1381.4.

--	--

	
The details of the preliminary analysis are provided in section 6.2 of the BI 754091 IB.

Rationale for change	More recent safety and efficacy information has been added to update the benefit-risk section of the protocol.
Section to be changed	1.4 BENEFIT – RISK ASSESSMENT
Description of change	Trial procedures such as blood sampling, imaging with e.g. contrast media, and tumour biopsies, are part of standard of care in these advanced cancer patients.
Rationale for change	The text was clarified to better describe the standard of care for advanced cancer patients.
Section to be changed	3.3.2 Inclusion Criteria
Description of change	3 Patient moving from one module to another must have prior irAEs resolved to a degree that would allow for restart of checkpoint inhibitor therapy according to the irAE management guidelines in the protocol.
Rationale for change	Text has been added to provide safety guidance when a patient moves from one Module to another.
Section to be changed	3.3.2 Inclusion Criteria
Description of change	Male patients with partners of childbearing potential must agree to use condoms and ensure their partners are using an additional highly-effective method of birth control, during the trial and until at least 6 months after the end of the trial treatment.
Rationale for change	The additional language provides guidance for male patients with partners of childbearing potential. This also aligns the text with the contraception requirements found in Section 4.2.2.3.
Section to be changed	3.3.3 Exclusion Criteria
Description of change	2 More than A maximum of one anti-PD-(L)1-based treatment regimen prior to entering study, more specifically defined in the modules.
Rationale for change	To help clarify the criteria
Section to be changed	3.3.3 Exclusion Criteria
Description of change	6. Patient has received allogeneic bone marrow or solid organ transplant.
Rationale for change	To address UK regulatory concern.
Section to be changed	3.3.3 Exclusion Criteria
Description of change	10 Active autoimmune disease or a documented history of autoimmune disease, except vitiligo or resolved

	childhood asthma/atopy, or a patient who was permanently discontinued removed from previous anti-PD-1 or anti-PD-L1 therapy because of a severe immune-related adverse event (irAE).
Rationale for change	To help clarify the criteria
Section to be changed	3.3.3.1 Withdrawal of patients from treatment or assessments
Description of change	The transition time between Modules (last dose of previous Module and screening visit of subsequent Module) will be a maximum of 2 months.
Rationale for change	The additional text provides further detail about transition timelines between Modules after progression on a previous treatment Module.
Section to be changed	4.1.3.1 Method of assigning patients to a second or subsequent, Module(s)
Description of change	The patient must sign an approved ICF for the subsequent Module, be screened prior to entering the new Module, and must meet all Master and Module-specific inclusion criteria. The transition time between Modules (last dose of previous Module and screening visit of subsequent Module) will be a maximum of 2 months. The assignment will be based on predefined algorithm if patients are eligible for more than one Module. Patients will be allowed multiple crossovers into subsequent Modules.
Rationale for change	The additional text provides further detail about how to cross a patient over to another Module after they have had progression on their previous treatment Module.
Section to be changed	Section 4.2.2.3 Contraception requirements
Description of change	WOCBP and men able to father a child must use two medically approved methods of birth control throughout the trial, and for a period of at least 6 months after last trial drug intake. WOCBP must use two highly effective methods of birth control per ICH M3 (R2) that result in a low failure rate of less than 1% per year when used consistently and correctly during the trial, and for a period of at least 6 months after the last dose of trial drug.
Rationale for change	The text was updated to correct the number of highly effective methods of birth control that should be used by a patient.

Section to be changed	Section 4.2.2.3 Contraception requirements
Description of change	Acceptable methods of birth control for this trial are: Highly-effective methods of contraception include:
Rationale for change	Redundant language was removed from the text.
Section to be changed	5.2.6.1.3 Adverse events of specific interest
Description of change	For this trial, infusion-related AEs, potential DILI events, hepatic injury, and qualifying irAEs, as defined in the treatment-specific Modules and Appendix 10.1, are AESIs.
Rationale for change	Language about drug-induced liver injury has been updated per BI revised template text to clarify that all liver elevations meeting potential Hy's Law criteria require expedited reporting as an AESI on the SAE form.
Section to be changed	5.2.6.1.3 Adverse events of specific interest
Description of change	In the event of an infusion-related reaction \leq Grade 2, the treat the symptoms accordingly with antihistamine or corticosteroids if needed. The infusion rate of BI 754111 and/or the combination of BI 754111 plus BI 754091 may be decreased by 50% or interrupted until resolution of the event and re-initiated at 50% of the initial rate until completion of the infusion. In patients experiencing infusion-related reactions \leq Grade 2, subsequent infusions may be administered at 50% of the initial rate. If an infusion-related reaction is Grade 3 or higher in severity at any point during the study, permanently discontinue study drug(s).
Rationale for change	Pre-treatment medication has been added to the study prior to administration of the study treatment in order to reduce the risk of infusion related reactions. In addition, more detail has been provided on what to do in the event of a Grade 3 or higher infusion related reaction.
Section to be changed	5.2.6.1.3 Adverse events of specific interest
Description of change	Hepatic injury and potential drug-induced liver injury (DILI)
Rationale for change	Language about drug-induced liver injury has been updated per BI revised template text to clarify that all liver elevations meeting potential Hy's Law criteria require expedited reporting as an AESI on the SAE form.
Section to be changed	5.2.6.1.3 Adverse events of specific interest

Description of change	
Hepatic injury definition: In patient with normal baseline hepatic function, hepatic injury is defined by the following alterations in hepatic laboratory parameters:
 
• An elevation of AST and/or ALT ≥ 3 times the ULN combined with an elevation of total bilirubin ≥ 2 times the ULN measured in the same blood draw sample, and/or• Marked peak AST and/or ALT elevation ≥ 10 times the ULN. 
A hepatic injury is defined by the following alterations of hepatic laboratory parameters:
 
• an elevation of AST (Aspartate Aminotransferase) and/or ALT (Alanine Aminotransferase) ≥ 3 fold ULN combined with an elevation of total bilirubin ≥ 2 fold ULN measured in the same blood draw sample, or• aminotransferase (ALT and/or AST) elevations ≥ 10 fold ULN. 
These lab findings constitute a hepatic injury alert and the patients showing these lab abnormalities need to be followed up according to the “Potential DILI Checklist” provided in the ISF.
 
In case of clinical symptoms of hepatic injury (icterus, unexplained encephalopathy, unexplained coagulopathy, right upper quadrant abdominal pain, etc.) without lab results (ALT, AST, total bilirubin) available, the investigator should make sure these parameters are analysed, if necessary in an unscheduled blood test. Should the results meet the criteria of hepatic injury alert, the procedures described in the “Potential DILI Checklist” (Figure 5.2.6.1.3: 1) should be followed.
 
Lab values meeting the hepatic injury definition will need to be reported as an AESI. Please follow the flowchart below for reporting hepatic injury / potential DILI cases.

------------------------------	---

	
Processing Potential DILI Cases in Oncology
 <pre> graph TD A[Lab values meeting the Hepatic Injury Definition in CTP] --> B[Report as AESI] B --> C[Uequivocal evidence of non-DILI etiology?] C -- No --> D[Complete all requirements of the DILI checklist] C -- Yes --> E[Further evaluation based on clinical judgement. Not necessary to complete all requirements of the DILI checklist***] </pre> 
* Such as PD, viral hepatitis, and etc. ** Report as AESI even if PD is determined (PD exemption does not apply for Potential DILI cases) *** Mark on DILI checklist that hepatic injury is due to a non-DILI etiology, such as PD, and submit DILI checklist & supporting source documents with SAE form

Rationale for change	A decision tree is provided to illustrate when the Potential DILI Checklist is initiated and when it can be considered complete.
Section to be changed	5.2.6.2.4 Pregnancy
Description of change	Similarly, potential drug exposure during pregnancy must be reported if a partner of a male trial participant becomes pregnant. This requires a written consent of the pregnant partner; Reporting and consenting must be in line with local regulations. The ISF will contain the trial specific information and consent for the pregnant partner.
Rationale for change	Guidance for the pregnant partner of a male trial participant was added.
Section to be changed	5.2.6.2.5 Exemptions to SAE Reporting
Description of change	5.2.6.2.5 Exemptions to AE/SAE Reporting
Rationale for change	The header has been corrected to reflect the section content.
Section to be changed	5.2.6.2.5 Exemptions to AE/SAE Reporting
Description of change	Lab values meeting the hepatic injury definition as defined in section 5.2.6.1.3 will need to be reported as AESI. PD reporting exemption does not apply to hepatic injury.
Rationale for change	Text stating that PD reporting exemptions do not apply to hepatic injury reporting was added for clarification. Language added to clarify that liver injury is to be reported as an AESI.
Section to be changed	6.1.2 Medical history

Description of change	Baseline PD-L1 expression level, microsatellite instability (MSI), and tumour mutation burden (TMB) information will be collected in eCRF, if locally available.
Rationale for change	Additional baseline data for a deeper analysis was added.
Section to be changed	7.3 Planned Analyses
